9.1.1.4 Photography of NLFs

Sites will receive a photography manual that describes how photographs will be standardized and managed. Photographs will be taken at Visit 2 (Baseline prior to treatment), Vist 4 and Vist 5.

9.1.2 Safety Assessments

9.1.2.1 Adverse Events

All adverse events (AEs) reported by study subjects, investigators, or other study staff through this study will be recorded.

If a serious AE or unanticipated serious device-related effect occurs, study subjects should return to the site for an unscheduled visit. Additionally, AEs will be assessed at every visit.

9.1.2.2 Injection Site Reaction Subject Diaries

Following initial treatment and optional touch-up injection(s), a 30 day take-home patient diary will be dispensed. The subject will record daily any site injection reactions. Take-home diaries will be returned to the site at next visit.

Investigators will review the Injection Site Reaction Diaries and determine if any of the reactions should be recorded in the eCRF as AEs.

9.1.2.3 Clinical laboratory Tests and Serum Pregnancy Tests

Non-fasting clinical laboratory tests will be performed at Visit 1 (Screening), Visit 5 (Month 6), and Visit 7 (End of Study). These labs include hematology, urine test and biochemistry to rule out any underlying disease that may exclude the subject from participation.

Serum pregnancy test will be performed on all women of childbearing potential at Visit 2 (Baseline), Visit 5 (Month 6) and at Visit 7 (End of Study).

Visit 1 (Screening) and Visit 2 (Baseline) maybe conducted on the same day if laboratory results are available and assessed by the investigator prior to treatment. If the serum pregnancy test results cannot be provided on the same day on Visit 2 (prior to injection) then the serum pregnancy test may be performed within 3 days before baseline visit so that a negative result is available prior to injection. Serum pregnancy results must be available prior to injection.

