7.2 Inclusion Criteria

Only Chinese adult subjects meeting all of the following inclusion criteria will be considered for study enrollment:

- 1. Is 22 65 years of age.
- 2. Has symmetrical NLFs of moderate or severe intensity (grade 3 or 4) on WSRS grade as determined by the independent blinded evaluator and confirmed by the treating investigator at baseline.
- 3. Both folds must have the same NLF score at baseline.
- 4. Has signed an informed consent.
- 5. Understands and accepts the obligation not to receive any other facial procedures below the eyes during the study.
- 6. Understands and accepts the obligation to present for all scheduled follow-up visits and is logistically able to meet all study requirements.
- 7. Subjects of childbearing potential must have a negative pregnancy test result and must not be lactating at the Screening/Baseline Visit and be willing and able to use an acceptable method of birth control (e.g. barrier methods used with a spermicidal agent, hormonal methods, IUD, surgical sterilization, abstinence) during the study. Women will be considered if one of the following conditions is documented on the medical history:
 - a. Postmenopausal with last menstrual bleeding at least 12 months prior to study; and
 - b. Without a uterus and/or both ovaries.

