7.4 Removal of Subjects from Treatment or Assessment

7.4.1 Discontinuation of Subjects

A subject may discontinue from the study at any time without any penalty or loss of benefits to which the subject is otherwise entitled. Date and discontinuation circumstances will be recorded.

Subjects must be discontinued from the study by the investigator at any time for any of the following reasons:

- Withdrawal of informed consent.
- Any AE for which the subject would be unable to continue in the study.
- Any subject who becomes pregnant may complete the study and will be followed for safety assessments.

Before discontinuation, every effort should be made to ensure that the subject returns for a final study visit. In the case of loss to follow-up subjects, every effort should be made to contact any subject lost to follow-up, and all such efforts should be documented in the subject file. If appropriate, according to local regulations, Ethic Committee(s) (EC) and Competent Authorities should be informed.

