- Safety of RADIESSE[®] injectable implant for use during pregnancy, in breastfeeding females or in patients under 18 years has not been established.
- The safety of RADIESSE[®] injectable implant in patients with increased susceptibility to keloid formation and hypertrophic scarring has not been studied.
- The safety of RADIESSE[®] injectable implant with concomitant dermal therapies such as epilation, UV irradiation, or laser, mechanical or chemical peeling procedures has not been evaluated in controlled clinical trials.
- Injection of RADIESSE[®] injectable implant into patients with a history of previous herpetic eruption may be associated with reactivation of the herpes.
- No studies of interactions of RADIESSE[®] injectable implant with drugs or other substances or implants have been conducted.
- Safety and effectiveness in the periorbital area has not been established.
- The patient should be informed that he or she should minimize exposure of the treated area to extensive sun or heat exposure for approximately 24 hours after treatment or until any initial swelling and redness has resolved.
- Universal precautions must be observed when there is a potential for contact with patient body fluids. The injection session must be conducted with aseptic technique.
- RADIESSE[®] injectable implant is packaged for single patient use. Do not resterilize. Do not use if package is opened or damaged. Do not use if the syringe end cap or syringe plunger is not in place.

- To help avoid needle breakage, do not attempt to straighten a bent needle. Discard it and complete the procedure with a replacement needle.
- Do not reshield used needles. Recapping by hand is a hazardous practice and should be avoided.
- After use, treatment syringes and needles may be potential biohazards. Handle accordingly and dispose of in accordance with accepted medical practice and applicable local, state and federal requirements.

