9.2.2 Data Collected

Visit 1 (Screening, Day -14 to Day 0)

The following data will be collected:

- Obtain informed consent
- Evaluate inclusion/exclusion criteria
- Subject demographics
- Vital signs: heart rate, blood pressure, and respiration rate
- Height
- Weight
- Laboratory Assessments: hematology, urine test and biochemistry
- WSRS scale assessment
- Medical history

- Concomitant Medications/Treatments
- Collect adverse events (AEs) and assess AEs

Visit 2 (Baseline/Initial Treatment, Day 1)

Screening and baseline visits may occur on the same day if laboratory test results are available prior to treatment.

The following data will be collected:

- Evaluate inclusion/exclusion criteria
- Weight
- Vital signs: heart rate, blood pressure and respiration rate
- Serum Pregnancy test for women of childbearing potential only
- Concomitant Medications/Treatments
- WSRS scale assessment
- Photograph(s) (pre-treatment)
- Randomization assignment for each NLF
- Dermal filler injections
- •
- Injection Site Reaction diary dispensed
- Collect AEs and assess AEs

Visit 3 (Week 4 / Month 1, Post Treatment; optional touchup, Day 28+ 7days)

Subjects may receive an optional touch-up injection at the 4-week post-treatment visit in order to achieve optimal correction. If touch-up is required on one or both NLFs, investigators must use the same NLF filler product as received during the initial treatment per the randomization schedule and must maintain the blind.

The following data will be collected:

- Vital signs: heart rate, blood pressure, and respiration rate

- Collect Injection Site Reaction diary and assess for AEs
- Concomitant Medications/Treatments
- If touch-up is required on one or both NLFs
 - Obtain original randomization assignment for each NLF
 - Dermal filler injections
 - -
 - Site Reaction diary dispensed
- Collect AEs and assess AEs

Visit 4 (Month 3 ± 7 days)

The following data will be collected:

- Collect Injection Site Reaction diary (if touch-up done at Visit 3) and assess for AEs
- Collect AEs and assess AEs
- Concomitant Medications/Treatments
- Photograph(s)

The following data will be collected:

- Vital signs: heart rate, blood pressure, and respiration rate
- Laboratory Assessments: hematology, urine test and biochemistry
- Weight

- WSRS scale assessment
- Photograph(s)
- Blinded evaluator GAIS

- Serum pregnancy test, for females of childbearing potential
- Collect AEs and assess AEs
- Concomitant Medications/Treatments

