9.2.3 Overview of Study Activity/Visit Schedule

				VISIL Scheuul	•		
Assessment	Visit schedule						
	Visit 1	Visit 2	Visit 3	Visit 4	Visit 5	Visit 6	Visit 7
Timepoint	Day 0 ¹ (Day -14 to Day 0)	Day 1 ¹	Week 4 /Month 1 (Day 28 + 7 d)	Month 3 ±7 d	Month 6 ±7 d	Month 9 ±7 d	Month 12 ± 7 d
	Screening	Baseline/ Initial	Touch-up ² (optional)				
	Effectiveness & Safety Follow-up						
Inclusion/Exclusion	X	X					
Informed consent	X						
Subject demographics	X						
Vital signs ³	Х	X	Х		Х		Х
Height	Х						
Weight	Х	Х			Х		Х
Laboratory assessment ⁴	х				Х		Х
Obtain randomization		Х					
Dermal filler injection		Х	X ⁵				
WSRS scale assessment					Х		
Photographs		Х		Х	Х		
Blinded Evaluator GAIS					Х		
Injection Site Reaction diary dispensed		х	X ⁷				

Table 4 Visit Schedule

Merz North America, Inc.

CLINICAL STUDY PROTOCOL Protocol # M900311004; Version1.3 (27-Jul-2018)

Assessment	Visit schedule								
	Visit 1	Visit 2	Visit 3	Visit 4	Visit 5	Visit 6	Visit 7		
	Day 0 ¹ (Day -14 to Day 0)	Day 1 ¹	Week 4 /Month 1 (Day 28 + 7 d)	Month 3 ± 7 d	Month 6 ±7 d	Month 9 ±7 d	Month 12 ± 7 d		
Timepoint	Base Screening Ini	Baseline/ Initial	Touch-up ² (optional)						
		Treatment	Effectiveness & Safety Follow-up						
Collect Injection Site Reaction diary			х	X ⁷					
Collect AEs and assess AEs	x	х	х	х	х	х	х		
Serum Pregnancy test ⁸		X ⁹			X		Х		
Medical history	Х								
Concomitant Medications/Treatments	x	х	х	х	x	х	х		

¹Screening (Day 0) and baseline (Day 1) may occur on the same day (if laboratory results are available prior to treatment).

² Subjects may receive an optional touch-up in order to achieve optimal correction at Week 4.

³Vital signs: heart rate, blood pressure, and respiration rate.

⁴ Laboratory Assessments include hematology, urine test and biochemistry.

⁵ If touch-up is required, the treatment investigators must use the same product on the NLF as that of the initial treatment per the randomization schedule.

•

⁷ If touch-up is required, Injection Site Reaction diary should be dispensed at Week 4 and collected at Month 3.

⁸Only for female subjects of childbearing potential (e.g. not post-menopausal for at least one year or has not had a hysterectomy or tubal ligation).

⁹ If the serum pregnancy test results cannot be provided on the same day on Visit 2 (prior to injection) then the serum pregnancy test may be performed within 3 days before baseline visit so that a negative result is available prior to injection.

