In the event of repeated non-compliance, as determined by the Sponsor, a Sponsor's monitor or company representative will attempt to secure compliance by one or more of the following (and not limited to):

- Visiting the investigator
- Telephoning the investigator
- Corresponding with the investigator

Repeated non-compliance with the signed agreement, the protocol or any other conditions of the study may result in further escalation in accordance with the Sponsor's written procedures including securing compliance or, at its sole discretion; Sponsor may terminate the investigator's participation in the study.

Confidential and Proprietary Information. Do not disclose without authorization.

14.2 **Protocol Amendments**

Approved protocol amendments will be provided to the Investigators by the Sponsor prior to implementing the amendment. The Principal Investigator is responsible for notifying the EC of the protocol amendment (administrative changes) or obtaining EC's approval of the protocol amendment (changes in subject care or safety), according to the instructions provided by the Sponsor with the protocol amendment.

Acknowledgement/approval by the EC of the protocol amendment must be documented in writing prior to implementation of the protocol amendment. Copies of this documentation must also be provided to the Sponsor.

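### The Week 4 touch-up is an injection visit with no pregnancy test and no rule in the protocol body to withhold it in pregnancy, although the first injection needs a negative result

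*Protocol*

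**What the plan says.** Section 9.1.2.3 schedules serum pregnancy tests for women of childbearing potential "at Visit 2 (Baseline), Visit 5 (Month 6) and at Visit 7 (End of Study"). The same section lets the baseline sample be drawn up to 3 days early so that a negative result is in hand, and closes with "Serum pregnancy results must be available prior to injection". A footnote to the visit schedule in 9.2.3 (Table 4) repeats the allowance and ties it to the first injection: "If the serum pregnancy test results cannot be provided on the same day on Visit 2 (prior to injection").

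A second injection can follow at Visit 3, Day 28 + 7 days. Section 9.2.2 states: "Subjects may receive an optional touch-up injection at the 4-week post-treatment visit". The only stated condition is the need for optimal correction, and the only stated constraints are that the same product be used and the blind kept.

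The other provisions that touch on pregnancy are:

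- **7.2, criterion 7:** a negative test at Screening/Baseline, and subjects must "be willing and able to use an acceptable method of birth control" during the study.
- **7.4.1:** "Any subject who becomes pregnant may complete the study and will be followed for safety assessments".
- **8.1.1.4, Precautions:** safety of Radiesse "for use during pregnancy, in breastfeeding females or in patients under 18 years has not been established".
- **10.7:** reporting of pregnancies within 24 hours, and follow-up of their outcome.

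**The concern.** The protocol sets its own standard, which is that no filler is injected until a negative result is available. It then applies that standard to only one of its two injection visits. The reason for the baseline test, that safety in pregnancy is not established, applies equally four to five weeks later.

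At stake is an elective injection given to a woman whose pregnancy neither she nor the injector knows about. She already carries both fillers from Visit 2, so the added exposure is the touch-up volume only. The point concerns subject protection. It does not bear on the per-protocol set, the sample size or the non-inferiority analysis.

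**Working it through.** The plan gives no figure to reproduce. The check compares the injection visits with the test visits, then looks for any other barrier at Visit 3.

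**Visits side by side (9.1.2.3, 9.2.2, Table 4)**

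| Visit | Injection | Pregnancy test |
|---|---|---|
| 2 (Day 1) | Yes | Yes |
| 3 (Day 28 to 35) | Optional touch-up | No |
| 5 (Month 6) | No | Yes |
| 7 (Month 12) | No | Yes |

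One of the two injection visits has a test. The sentence in 9.1.2.3, the visit lists in 9.2.2 and the pregnancy row of Table 4 all agree.

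**Other barriers at Visit 3**

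- Eligibility is reviewed at Visits 1 and 2 only (Table 4).
- Criterion 7 ties the negative test to Screening/Baseline.
- Adverse events and concomitant medications are reviewed at Visit 3. That can bring out a pregnancy the subject knows of, but not one she does not.
- Section 7.4.1 allows a pregnant subject to complete the study and is silent on further injections. The sentence also sits in a list of reasons for mandatory discontinuation, which makes its meaning harder to read.
- Section 10.7 deals with reporting and follow-up, not with withholding treatment.
- Pregnancy is a precaution for Radiesse in 8.1.1.4. It is not among the contraindications for either product (8.1.1.4, 8.1.2.4).

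**Age of the last result at the touch-up**

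- Shortest: 28 − 1 = 27 days (test on Day 1, touch-up on Day 28).
- Longest: (35 − 1) + 3 = 37 days (touch-up on Day 35, sample drawn 3 days before baseline).

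**Illustrative number of conceptions between Visits 2 and 3**

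Only the 174 subjects and the visit days come from the documents. The other rates are assumptions: 50% to 90% of subjects of childbearing potential, and 1% to 10% pregnancies per year on contraception.

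Expected number = subjects × share of childbearing potential × annual rate × days / 365.25

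- Low: 174 × 0.5 × 0.01 × 27 / 365.25 = 0.064
- High: 174 × 0.9 × 0.10 × 34 / 365.25 = 1.458

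This counts conceptions, not re-injections prevented. The preventable number is lower, because some women need no touch-up, some pregnancies will already be known, and some conceptions will be too recent to test positive.

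**The case against.** The case for leaving the plan alone has five parts.

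1. **The closing sentence of 9.1.2.3 names no visit**, so it could be read to cover the touch-up. That reading fails in practice. The paragraph is about Visits 1 and 2, and no test is scheduled at Visit 3 to supply a result. If the sponsor intends it, the schedule still has to be corrected.
2. **Safeguards already exist.** Contraception is required, the precaution is printed in the protocol, a known pregnancy must be reported, the touch-up is optional, and nothing directs an investigator to inject a woman known to be pregnant. This is fair for a recognised pregnancy. It leaves the unrecognised one uncovered. Contraception is also required of the women tested at Visits 2, 5 and 7, so the protocol does not treat it as a substitute for testing.
3. **The instructions for use (Appendices 1 and 2) may contain a withholding instruction.** They were not in the text reviewed, so this stands as a limit: the statement that no such rule exists covers the protocol body only. Without a test, such an instruction would still not reach an unrecognised pregnancy.
4. **The risk is small.** Pregnancy is not a listed contraindication, the protocol describes no fetal hazard, and the upper figure combines two generous assumptions. All of this stands and limits the weight of the point.
5. **Table 4 is weak evidence.** In the text reviewed, its WSRS row omits visits that 9.2.2 lists, and parts of the Visit 3 list are blank. The omission does not depend on the table, however. The sentence in 9.1.2.3 is intact and leaves Visit 3 out.

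**Conclusion.** The concern holds. The protocol requires a negative pregnancy result before the first injection, schedules none before the second, and has no rule in its body to withhold the touch-up in pregnancy. At the touch-up the last result is 27 to 37 days old.

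The expected number of conceptions in the interval, 0.06 to 1.46 among 174 subjects, rests wholly on assumed rates and overstates what a test would prevent. The remaining exposure is confined to unrecognised pregnancies and to the touch-up volume. The change should be made because it closes a gap against the protocol's own standard at little cost, not because many women are likely to be affected. It helps only while touch-ups remain to be given.

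**What to change.** 1. **Section 9.1.2.3:** add *Before any touch-up at Visit 3, women of childbearing potential must have a negative pregnancy test (urine at the visit, or serum at the visit or within 3 days before). No touch-up is given if the result is positive.*
2. **Section 9.2.2, Visit 3:** make this test the first item under the touch-up steps. In Table 4, mark the Visit 3 cell of the pregnancy row with the footnote *only if a touch-up is to be given; urine or serum*.
3. **Section 7.4.1:** state in the pregnancy sentence that such a subject receives no further injection, keeping the existing permission to complete the study with safety follow-up.

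The third change alone would settle known pregnancies. The first two are needed for unknown ones.

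**Cost:** a protocol amendment. Section 14.2 requires the ethics committee's "approval of the protocol amendment (changes in subject care or safety"), which applies here. The added testing is at most one test per woman of childbearing potential who is to have a touch-up, so no more than 174 tests. With a urine test at the visit, there is no extra attendance and no need to test women who turn out not to want or need a touch-up.

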9.1.2.4 Vital Signs

Vital signs will be measured on subjects after they have been seated for about 5 minutes. Resting heart rate, blood pressure (systolic and diastolic, preferably on the same arm each time) and respiration rate will be measured at Visits 1, 2, 3, 5 and 7.

Demographic information will be collected at Screening for all subjects and recorded in the eCRF. Demographic information includes age gender, race, weight, height and Fitzpatrick skin type. This will be collected according to local rules and regulations. Weight will also be collected at Visits 2, 5, and 7.

9.1.3.3 Medical History, prior/concomitant medication and non-drug therapy

Medical history, prior/concomitant medication and non-drug therapy relevant to inclusion/ exclusion criteria and restrictions will be collected as part of the screening assessment regardless of onset time. Findings will be recorded in the eCRF.

9.2 Visit Schedule

9.2.1 Study Time Points

The planned study period is 12 Months consisting of the following visits:

- Visit 1 (Screening): Screening and Baseline Visits may be the same day (if laboratory results are available prior to treatment)
- Visit 2 (Baseline/Treatment): Day 1, Injection
- Visit 3 (Week 4 / Month 1 Post Treatment): Optional touch-up with the same randomized product
- Visit 4 (Month 3 Post Treatment)
- Visit 5 (Month 6 Post Treatment): Primary endpoint
- Visit 6 (Month 9 Post Treatment)
- Visit 7 (Month 12 Post Treatment)

9.2.2 Data Collected

Visit 1 (Screening, Day -14 to Day 0)

The following data will be collected:

- Obtain informed consent
- Evaluate inclusion/exclusion criteria
- Subject demographics
- Vital signs: heart rate, blood pressure, and respiration rate
- Height
- Weight
- Laboratory Assessments: hematology, urine test and biochemistry
- WSRS scale assessment
- Medical history

- Concomitant Medications/Treatments
- Collect adverse events (AEs) and assess AEs

Visit 2 (Baseline/Initial Treatment, Day 1)

Screening and baseline visits may occur on the same day if laboratory test results are available prior to treatment.

The following data will be collected:

- Evaluate inclusion/exclusion criteria
- Weight
- Vital signs: heart rate, blood pressure and respiration rate
- Serum Pregnancy test for women of childbearing potential only
- Concomitant Medications/Treatments
- WSRS scale assessment
- Photograph(s) (pre-treatment)
- Randomization assignment for each NLF
- Dermal filler injections
- •
- Injection Site Reaction diary dispensed
- Collect AEs and assess AEs

Visit 3 (Week 4 / Month 1, Post Treatment; optional touchup, Day 28+ 7days)

Subjects may receive an optional touch-up injection at the 4-week post-treatment visit in order to achieve optimal correction. If touch-up is required on one or both NLFs, investigators must use the same NLF filler product as received during the initial treatment per the randomization schedule and must maintain the blind.

The following data will be collected:

- Vital signs: heart rate, blood pressure, and respiration rate

- Collect Injection Site Reaction diary and assess for AEs
- Concomitant Medications/Treatments
- If touch-up is required on one or both NLFs
 - Obtain original randomization assignment for each NLF
 - Dermal filler injections
 - -
 - Site Reaction diary dispensed
- Collect AEs and assess AEs

Visit 4 (Month 3 ± 7 days)

The following data will be collected:

- Collect Injection Site Reaction diary (if touch-up done at Visit 3) and assess for AEs
- Collect AEs and assess AEs
- Concomitant Medications/Treatments
- Photograph(s)

The following data will be collected:

- Vital signs: heart rate, blood pressure, and respiration rate
- Laboratory Assessments: hematology, urine test and biochemistry
- Weight

- WSRS scale assessment
- Photograph(s)
- Blinded evaluator GAIS

- Serum pregnancy test, for females of childbearing potential
- Collect AEs and assess AEs
- Concomitant Medications/Treatments

Visit 6 (Month 9 ± 7 days)

The following data will be collected:

- Collect AEs and assess AEs
- Concomitant Medications/Treatments

Visit 7 (Month 12 ± 7 days)

The following data will be collected:

- Vital signs: heart rate, blood pressure, and respiration rate
- Weight
- Laboratory assessments: hematology, urine test and biochemistry
- Serum Pregnancy test for women of childbearing potential only

_	

• Collect AEs and assess AEs

• Concomitant Medications/Treatments

